6.2.4. Safety monitoring and individual stopping rules

Safety data to be recorded:

- vital signs: blood pressure (systolic and diastolic) and heart rate will be measured daily the patient him/herself using an electronic device. BP and HR measurements will be done with the subject comfortably seated on a chair, with the middle of the cuff on the upper arm at the level of the right atrium (the midpoint of the sternum). Also the body temperature will be measured by 10:00 am using an electronic device.
- SpO₂ will be measured by transdermal oximetry to be collected once daily concomitantly with the BP / HR measurement.
- laboratory tests will be performed on venous blood samples taken from the patient at domicile (drawings performed by a nurse sent to the patient's domicile and delivered to the study site's laboratory). The lab results should be reviewed by the Investigator and clinically relevant changes recorded as AEs. Training to the personell in charge of the samples collection and delivering to the laboratory, and instructions to the laboratory personnel for reporting the lab assessments will be performed at the initial site visit.

Any sign or symptom associated to adverse events will be reported by the patient in an electronic patient diary EXOM GENIUS ROSA and reported during the telemedicine consult. The eDiary should be filled in daily by the patient by 09:00 pm.

All patients will be withdrawn from the study when criteria for supplemental oxygen therapy and/or mechanical ventilation are met. Another stopping rule (patient's withdrawal from study) includes drug related adverse events grade ≥ 3 according to Common Terminology Criteria for Adverse Events (CTCAE) version 5.0 [Common Terminology Criteria for Adverse Events (CTCAE) Last Updated: 03/01/18 available at https://ctep.cancer.gov/protocolDevelopment/electronic_applications/ctc.htm]

Patients are free to withdraw from participation in the study at any time upon request, without any consequence. Patients should be listed as having withdrawn consent only when they no longer wish to participate in the study and no longer authorize the Investigators to make efforts to continue to obtain their outcome data. Every effort should be made to encourage patients to remain in the study for the

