8.4. SERIOUS ADVERSE EVENT REPORTING

8.4.1. Reporting Procedure for Investigators

The investigator must report all SAEs, regardless of presumed causal relationship to Study Safety Contact (i.e. Dompé Pharmacovigilance and Contract Research Organization Pharmacovigilance expert) recording the SAE data on the AEs section of the eCRF within 24 hours of learning of the event. The paper SAE forms are only intended as a back-up option when the eCRF system is not accessible. In this case, the original paper forms are to remain on site and copies are to be transmitted via email or confirmed facsimile (fax) transmission to:

- e-mail address: [contact]
- [contact]

Contact details for SAE reporting are provided in the section "Contact Information".

The investigator should also report information on SAEs that continue after patient has completed his/her participation in the study (whether study completion or withdrawal), unless patient has withdrawn his/her consent.

Information on SAEs will be recorded on the AEs section form in the eCRF. Follow-up reports (as many as required) should be completed following the same procedure; the system will mark the SAE form as "Follow up no. XX"

Whenever more than one SAE is observed, the Investigator should identify which is the primary adverse event, i.e. the most relevant one. If other events are listed in the same report, the Investigator, along with their relatedness to the Investigational Product, should identify which adverse events are serious and which are non-serious. In any case, the Investigator is requested to record his/her opinion about the relatedness of the observed event(s) with the investigational medication.

In line with CT3 Detailed Guidance and ICH E2A provisions, although the Investigator does not usually need to actively monitor patients for AEs once the trial has ended, if the Investigator becomes aware of

a SAE occurring to a patient after that patient has ended his/her participation in the study (whether study completion or withdrawal), the SAE should be reported by the Investigator using the following email address: [contact] or [contact]. Such “post-study cases” should be regarded for expedited reporting purposes by Dompé, as though they were study reports. Therefore, a causality assessment and determination of expectedness are needed for a decision on whether or not expedited reporting is required.

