9.5.2.2. Secondary analyses

All secondary endpoints will be analyzed at each available timepoints by means of descriptive statistics and by appropriate parametric tests depending on the nature of the variable and its distribution. Data transformation might be used in order to satisfy the assumption of normality requested by parametric statistical tests. In case such assumptions are not met, non-parametric counterpart tests will be used. Change from baseline value (for continuous variables) and shift tables versus baseline (for categorical variables) will also be summarized for all post-baseline visits.

The incidence of participants with undetectable SARS-CoV-2 at PCR, the incidence of participants who requires supplemental oxygen therapy (NEWS ≤ 2) and/or mechanical ventilation, and mortality will be analyzed as proportion at each time point and as time-to-event.

Details will be provided in the SAP.

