4.4 OVERALL ANALYSIS

Final analyses identified in this SAP will be performed by Agati Clinical Informatics following Sponsor Authorization of this Statistical Analysis Plan, Database Lock, Sponsor Authorization of Analysis Population and Unblinding of Study Treatment.

For primary and secondary efficacy endpoints, p-value, lower and upper 95% Confidence Limits (CL) will be also presented based on the statistical analysis performed.

The default summary statistics for quantitative variables will be the number of observations (n), mean, standard deviation (SD), median, minimum (min) and maximum (max).

For qualitative variables, the number (n) and percentage (%) of patients with non-missing data per variable of interest will be the default summary presentation, if appropriate and wherever required the number of missing values will be presented as a "Missing" category. If appropriate, 95% confidence intervals around the percentage will be presented.

Time-to-event endpoints will be assessed by the Kaplan-Meier (K-M) method. Time to event curves will be compared (i.e comparisons of each active treatment group versus placebo) using log-rank test and estimates of hazard ratio will be obtained using Cox proportional hazards model after performing diagnostics of proportional hazard assumption (investigated with a time dependent exploratory variable treatment*{log[time to event]}); if the p-value from the Wald Chi-squared statistic for this variable is less than 5% there is evidence of a departure from the adjusted model assumptions.). K-M estimates of median survival time associated with each treatment group will be provided along with 25th and 75th percentiles and their 2-sided 95% CIs (based on Greenwood's method). K-M estimates will be presented at Day 7, 14 and 28 for each treatment group. K-M curves will be plotted comparing treatment groups with the number of patient-at-risk in each treatment group at exact time points. Patients who are ongoing and who are free from event at the time of DB lock will be censored at the DB lock date. Patients who have discontinued without an event will be censored at the date of discontinuation. Patients who are died will be considered as censored with death

date as date of censored.

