In the SAS® procedure PROC GENMOD, a Type III analysis will be performed by adding the model options: TYPE3, DIST=BIN and LINK=LOGIT. REPEATED statement will be used to consider visit and TYPE=UN option used for correlation-matrix. If the model does not converge then appropriate TYPE would be applied for correlation-matrix.

The following time-to-event endpoints will be analysed according to SAP section 4.4 methods.

- i. Time to reach undetectable SARS-CoV-2 at PCR
- ii. Time to get relieved from supplemental oxygen therapy (NEWS ≤ 2) and/or mechanical ventilation
- iii. Overall survival

Analyses will be performed on FAS population.

3. Proportion of patients in each NEWS category at Day 7, 14 and 28 after randomization will be summarized by frequency and percent by treatment and visit for FAS population.
4. NEWS score at Day 7, 14 and 28 after randomization will also be summarized using descriptive statistics by treatment and visit for FAS population.
5. Proportion of hospitalized patients who at the beginning of the study were at domicile isolation at day 7, 14 and 28 after randomization will be analysed using comparison of proportions (i.e comparisons of each active treatment group versus placebo at each assessment day) through Fisher's exact test and will be summarized using frequency and percent by treatment and visit. Analyses will be performed on FAS population.

6. Proportion of patients admitted to intensive care at Day 7, 14 and 28 after randomization will be analysed using comparison of proportions (i.e comparisons of each active treatment group versus placebo at each assessment day) through Z-test and will be summarized using frequency and percent by treatment and visit. Analyses will be performed on FAS population.
7. Overall survival will be analysed according to time-to-event methods described in SAP section 4.4.
8. Quality of life questionnaire (EQ-5D-5L) at 3 months after the randomization will be summarized using appropriate descriptive statistics by treatment. The number and proportion of subjects of each level (1 - no problems, 2 - slight problems, 3 - moderate problems, 4 - severe problems, 5 - extreme problems) for each dimension (mobility, self-care, usual activities, pain/discomfort, and anxiety/depression) will be reported.
Analyses will be performed on FAS population.

Patient's data will be listed for all secondary endpoints.

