14.1.3 DERIVATION

Pre-menopausal status – Female patients with child-bearing potential will be considered.

Post-menopausal status – Female patients with non-child-bearing potential will be considered.

Status – Male, Female with pre-menopausal status and Female with post-menopausal status will be considered for “Status” variable derivation for the Analysis.

Time to reach undetectable SARS-CoV-2 at PCR:

Patients who have experienced the event (undetectable SARS-CoV-2 at PCR), their date of PCR result confirmation will be used for time duration calculation.

Time to reach undetectable SARS-CoV-2 at PCR = (Date of undetectable SARS-CoV-2 at PCR / Censored date – Treatment Start date) + 1

Time to get relieved from supplemental oxygen therapy (NEWS ≤ 2) and/or mechanical ventilation:

Patients who have experienced the event (relieved from supplemental oxygen therapy (NEWS ≤ 2) and/or mechanical ventilation), their date of confirmation will be used for time duration calculation.

Time to get relieved from supplemental oxygen therapy (NEWS ≤ 2) and/or mechanical ventilation = (Date of relieved from supplemental oxygen therapy (NEWS ≤ 2) and/or mechanical ventilation / Censored date - Treatment Start date) + 1

Overall Survival:

Overall Survival = (Date of Death / Censored date - Treatment Start date) + 1

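### SAP 4.4, as applied to overall survival, censors deaths and may censor at clinical deterioration; the protocol's mortality proportion is dropped without being listed as a change

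*SAP*

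**What the plan says.** Protocol 7.1.2 and SAP 3.2.2 list the proportion of survivors at days 7, 14 and 28 as a secondary endpoint. The rules that bear on it are these.

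- **SAP 14.1.2, item 7:** "Overall survival will be analysed according to time-to-event methods described in SAP section 4.4". No exception is made for this endpoint.
- **SAP 4.4, methods:** Kaplan-Meier, log-rank and Cox, and "K-M estimates will be presented at Day 7, 14 and 28 for each treatment group".
- **SAP 4.4, censoring at discontinuation:** "Patients who have discontinued without an event will be censored at the date of discontinuation".
- **SAP 4.4, deaths:** "Patients who are died will be considered as censored with death"; the sentence goes on to make the death date the censoring date.
- **SAP 14.1.3:** "Overall Survival = (Date of Death / Censored date - Treatment Start date) + 1".
- **Protocol 6.2.4:** "All patients will be withdrawn from the study when criteria for supplemental oxygen therapy and/or mechanical ventilation are met".
- **Protocol 9.5.2.2:** "and mortality will be analyzed as proportion at each time point and as time-to-event".

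Other sections point to longer follow-up. Protocol 6.3 keeps patients who stop the study drug in the study for efficacy and safety outcomes. Protocol 3.3 continues safety follow-up to the last planned visit after early discontinuation. SAP 7.3.2 gives disease progression as a reason for stopping treatment but not for leaving the study. SAP 15.1.2 separately tabulates deaths and adverse events leading to death, and lists deaths.

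**The concern.** Three things go wrong when section 4.4 is used for survival.

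First, the sentence on deaths suits an endpoint such as time to undetectable virus, where death ends observation before the event of interest. For overall survival, death is the event. The sentence carries no restriction, so a programmer who follows it codes every death as censored.

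Second, censoring at study discontinuation assumes that those who leave have the same later risk of death as those who stay. A patient who leaves on reaching oxygen or ventilation criteria plainly does not. If a drug changes progression, the proportion censored this way also differs by arm.

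Third, the protocol promised a simple proportion alongside the time-to-event analysis. The SAP specifies only the time-to-event analysis and does not record the omission among its changes from protocol.

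At stake is whether the efficacy survival result is right, and whether it agrees with the death count in the safety tables.

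**Working it through.** The documents give no event count, power or mortality assumption for survival, so there is no planned figure to reproduce. The check compares the rules and then illustrates size under stated assumptions.

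**1. The rule on deaths.** Take a patient who dies on study day 20. SAP 14.1.3 gives a survival time of 20 days. SAP 4.4 marks that time as censored. Applied to all deaths, the number of events is 0. Kaplan-Meier survival is then 100% at days 7, 14 and 28 in every arm, the log-rank statistic has zero numerator and zero variance, and the Cox hazard ratio cannot be estimated. This holds whatever the withdrawal rule.

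**2. The rule on discontinuation.** Protocol 9.1 assumes 50% (placebo) and 75% (active) recover without oxygen or ventilation by day 14. The complements are 1 − 0.50 = 50% and 1 − 0.75 = 25%. These are design assumptions, not forecasts, but they show that Protocol 6.2.4 could remove different proportions by arm.

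A simulation used these proportions, oxygen need spread evenly over days 1 to 14, an assumed 12% mortality after oxygen need with death 1 to 14 days later, and censoring at oxygen need:

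- No deaths without oxygen need: true 28-day mortality is 0.50 × 12% = 6.0% (placebo) and 0.25 × 12% = 3.0% (active). Kaplan-Meier shows 0% and 0%.
- Adding 0.6% mortality in patients who never need oxygen: true mortality is 6.3% and 3.5%. Kaplan-Meier shows 0.5% and 0.6%, with 5% and 13% of deaths counted.

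**3. Size with 68 patients (SAP 4.3).** The only death rates in the documents are background figures in Protocol 2.6 (2.8% and 4.7%; 8.2% and 14.8%). They are used here only as a range. Deaths in all = 68 × rate. Deaths in one active-placebo pair = 68 × 2/3 × rate, assuming equal arms. Power is by the Schoenfeld formula, Φ(√d × |ln 0.5| / 2 − 1.96), at an assumed hazard ratio of 0.5 and two-sided 5%. The last three columns give deaths counted in all 68 if the stated share follows oxygen need and is censored.

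| Death rate | Deaths in 68 | Per pair (d) | Power, full data | 50% censored | 80% censored | 100% censored |
|---|---|---|---|---|---|---|
| 2.8% | 1.9 | 1.3 | 5.8% | 1.0 | 0.4 | 0 |
| 4.7% | 3.2 | 2.1 | 7.3% | 1.6 | 0.6 | 0 |
| 8.2% | 5.6 | 3.7 | 9.8% | 2.8 | 1.1 | 0 |
| 14.8% | 10.1 | 6.7 | 14.4% | 5.0 | 2.0 | 0 |

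For 80% power, 66 events per pair would be needed.

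**4. The proportion.** Protocol 9.5.2.2 requires both forms of mortality analysis. SAP 14.1.2 specifies one. The day 7, 14 and 28 Kaplan-Meier estimates are not a substitute, because they inherit the censoring in steps 1 and 2. SAP section 18 lists four changes, and this is not among them.

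**The case against.** The strongest reply is that the withdrawal problem is one reading of conflicting text. Protocol 3.3 and 6.3 and SAP 7.3.2 point to continued follow-up, and SAP 14.1.2 plans a time to relief from oxygen, which presupposes observation after oxygen starts. Section 4.4 censors those who discontinue without an event, so a patient withdrawn on day 9 whose day-20 death is known could be said to have an event. This stands to the extent that the withdrawal route is conditional. It does not settle the matter: Protocol 6.2.4 is explicit, the premature-discontinuation list in 6.3 itself includes disease progression, and the SAP does not say how a death after withdrawal is scored.

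A reader might infer that survival is analysed by Kaplan-Meier alone, or that deaths vanish from the report. Neither is supported. Section 4.4 adds log-rank and Cox, and SAP 15.1.2 reports deaths separately. That second fact makes a contradiction between efficacy and safety tables possible; it does not repair the survival analysis.

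A reader might also infer that existing serious adverse event reports are enough for the repair. Protocol 8.1 makes every death a serious adverse event, and 8.4.1 says "The investigator should also report information on SAEs that continue after patient has completed his/her participation in the study". But new events after participation are reported only if the investigator becomes aware of them, and 8.4.3 exempts trial end points from such reporting. Completeness is not assured.

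Finally, this is a secondary endpoint in a trial stopped at 68 patients. That is true, and it limits what the repair can deliver.

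**Conclusion.** The survival analysis is wrong as written and should be corrected. The rule that censors deaths is the most direct defect: it contradicts SAP 14.1.3 and, applied literally, yields zero events under any follow-up rule. The discontinuation rule adds informative censoring if Protocol 6.2.4 is applied. The missing proportion is an unlisted departure from the protocol.

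It is tempting to conclude that the withdrawal rule by itself makes the mortality endpoint nearly blind. The documents do not support that as a settled finding. It needs Protocol 6.2.4 to prevail over the sections that conflict with it, and most deaths to follow oxygen need; the documents give no such share. Over the illustrative range, deaths counted run from 0 to 5.0 out of 1.9 to 10.1 when 50% to 100% of deaths are censored.

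Power would remain at about 6% to 14% after repair, on the assumed death rates and hazard ratio. The benefit is a correct mortality result that agrees with the safety tables, not a conclusive comparison.

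**What to change.** In SAP 4.4 and 14.1.2:

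- State that death is the event for overall survival, and limit the sentence that censors deaths to the other time-to-event endpoints.
- Count every known death to day 28 in FAS patients regardless of study status, and censor only at the last date known alive.
- Restore the proportion of survivors at days 7, 14 and 28 on the FAS, or list its removal in section 18.
- For ICU admission (item 6), state how patients with no status after withdrawal are classified. SAP section 17, item d, already gives the default denominator.

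Reconcile Protocol 6.2.4 with Protocol 3.3 and 6.3 and SAP 7.3.2, so that it is clear who remains under follow-up. This review takes no view on which withdrawal rule should apply.

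The cost is SAP wording plus a day-28 vital-status check for withdrawn patients before database lock. That check is real work, because serious adverse event reports alone may be incomplete, and counting only passively reported deaths would bring an ascertainment bias of its own.

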14.1.3 DERIVATION

Pre-menopausal status – Female patients with child-bearing potential will be considered.

Post-menopausal status – Female patients with non-child-bearing potential will be considered.

Status – Male, Female with pre-menopausal status and Female with post-menopausal status will be considered for “Status” variable derivation for the Analysis.

Time to reach undetectable SARS-CoV-2 at PCR:

Patients who have experienced the event (undetectable SARS-CoV-2 at PCR), their date of PCR result confirmation will be used for time duration calculation.

Time to reach undetectable SARS-CoV-2 at PCR = (Date of undetectable SARS-CoV-2 at PCR / Censored date – Treatment Start date) + 1

Time to get relieved from supplemental oxygen therapy (NEWS ≤ 2) and/or mechanical ventilation:

Patients who have experienced the event (relieved from supplemental oxygen therapy (NEWS ≤ 2) and/or mechanical ventilation), their date of confirmation will be used for time duration calculation.

Time to get relieved from supplemental oxygen therapy (NEWS ≤ 2) and/or mechanical ventilation = (Date of relieved from supplemental oxygen therapy (NEWS ≤ 2) and/or mechanical ventilation / Censored date - Treatment Start date) + 1

Overall Survival:

Overall Survival = (Date of Death / Censored date - Treatment Start date) + 1

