Appendix 1**Biochemistry (T0, T7, T14, T21, T28)**

Sodium
Potassium
Chloride
Urea
Uric acid
Creatinine
Calcium
Inorganic phosphorus
Fasting Glucose
Total and direct bilirubin
Total protein
Albumin
Alpha-1 Globulins
Alpha-2 Globulins
Beta Globulins
Alkaline phosphatase
AST
ALT
Gamma glutamyl transferase
Total Cholesterol
Triglycerides

Haematology (T0, T7, T14, T21, T28)

Haemoglobin
Red cell count
Packed cell volume
Mean cell volume
Mean cell haemoglobin
Mean cell haemoglobin concentration
Platelet count
White cell count
Neutrophils
Lymphocytes
Monocytes
Eosinophils
Basophils

Coagulation (T0, T7, T14, T21, T28)

Prothrombin time
Activated partial thromboplastin time
INR

Virology (T7, T14, T28)

PCR

Other markers (T0, T7, T14, T21, T28)

D-dimer;
Creatine phosphokinase (CPK);
Lactate dehydrogenase (LDH).

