6.2.2. Standard Patient monitoring

All patients will daily self-monitor their parameters and may call the Investigator if needed. In case the enrolled person cannot perform the daily self-monitoring, a close relative may support him, provided that all possible precautions and safety devices are used. Patients will be provided with individual electronic device for measuring blood pressure, heart rate, body temperature and transdermal SpO₂.

Patients will be also provided with an electronic patient diary in which report the information about the daily drug self-administration, the above mentioned parameters recorded, the AEs (if any) and the concomitant medications (if any).

The Investigator will remotely regularly assess NEWS and evaluate the need for immediate visit or hospitalization.

The Investigator will contact the General Practitioner who will decide to directly involve emergency service for immediate visits for critical patients presenting:

- A. SpO₂ ≤ 95%;
- B. Systolic blood pressure >180 mmHg or <100 mmHg
- C. Body temperature >39°C or less than 35.0 °C;
- D. Heart rate >110 bpm or less than 40 bpm;
- E. Sensorial deterioration according to doctor's judgment.

Patients will receive a Study Nurse visit at the day 0, 7, 14, 21 and 28.

At day 7, 14, 28 patients will be tested for viral shedding. At day 0, 7, 14 patients will undergo pregnancy test (female only). At day 0, 7, 14, 21, 28 patients will undergo blood test including hepatic function, renal function, coagulation, LDH, CPK and complete blood counts.

Venous blood samples (~ 20 mL) will be collected from a forearm vein.

Healthcare workers approaching COVID-19 patients will use personal protective equipment including a FFP3 (or FFP2) mask, gloves, gown and googles. FFP3 should be used always in case of any procedure on respiratory tract (including nasopharyngeal swab).

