7 GENERAL CONSIDERATIONS

7.1 REFERENCE START DATE AND STUDY DAY

In general, reference start date is defined as the day of the first dose of study medication (Study Day 1: first day) and will appear in every listing where an assessment date or event date appears.

Study Day will be calculated from the reference start date and will be used to show start / stop day of assessments and events.

If the date of the assessment/event is on or after the reference start date, then:

Study Day = (date of assessment/event – reference start date) + 1

If the date of the assessment/event is prior to the reference start date, then:

Study Day = (date of assessment/event – reference start date)

In the situation where the assessment/event date is partial or missing, the date will appear partial or missing in the listings, and Study Day and any corresponding duration will be presented based on the imputations specified in Appendix 2 (Partial Date Conventions).

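### The Kaplan-Meier day count for viral clearance can place on-time swabs after the Day 7, 14 and 28 landmarks at which the curve is read

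*SAP*

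**What the plan says.** - **Event date.** SAP 14.1.3, on time to undetectable PCR: "their date of PCR result confirmation will be used for time duration calculation". The formula beneath it ends "Censored date – Treatment Start date) + 1".
- **Day count.** SAP 7.1: "reference start date is defined as the day of the first dose of study medication (Study Day 1: first day". On or after that date, "Study Day = (date of assessment/event – reference start date) + 1". This scale has no day 0.
- **Visits.** Protocol 6.2.2 starts its scale at zero: "Patients will receive a Study Nurse visit at the day 0, 7, 14, 21 and 28". On the same scale, "At day 7, 14, 28 patients will be tested for viral shedding". The laboratory list in the protocol synopsis (Appendix 1) agrees: "Virology (T7, T14, T28". No PCR is listed at T0 or T21.
- **Landmarks.** SAP 4.4: "K-M estimates will be presented at Day 7, 14 and 28 for each treatment group".
- **Binary endpoints.** SAP 3.2 counts their days from randomisation, not from first dose.
- **NEWS/oxygen time endpoint.** SAP 14.1.3 uses the same formula with +1, and again refers to a date of confirmation.

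**The concern.** Event times are built on a scale that starts at 1 on the day of first dose. They are then read at day numbers taken from a visit scale that starts at 0. Dating the event by the PCR result instead of the swab can only move it later. A swab taken exactly on schedule may therefore be counted after the landmark that carries its name.

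At stake is the agreement of two outputs in one report. Protocol 9.5.2.2 wants viral clearance shown both as a proportion at each time point and as time-to-event. SAP 14.1.1 tabulates the PCR result by treatment and visit. A reader will expect the Day 7 Kaplan-Meier estimate to match the Day 7 proportion, because T7 is the first post-baseline swab. The nominal-visit rule in SAP 7.3.1 covers by-visit summaries only and does not reach the Kaplan-Meier times.

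**Working it through.** **Inputs.** Swab days v = 7, 14, 28 after T0 (Protocol 6.2.2). Time formula from SAP 14.1.3. Landmarks from SAP 4.4. Two quantities are not in the documents and are varied: d, the days from T0 to first dose, and L, the days from swab to PCR result. T0 is taken to be the day of randomisation.

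**Formula.** The first dose is on day d and the result on day v + L, so

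time = (v + L) − d + 1.

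An on-time swab misses landmark v when v + L − d + 1 > v. In whole days, that means L ≥ d.

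**Times for T7 / T14 / T28 swabs taken on schedule**

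| First-dose delay d | L = 0 | L = 1 | L = 2 |
|---|---|---|---|
| 0 | 8 / 15 / 29 (miss) | 9 / 16 / 30 (miss) | 10 / 17 / 31 (miss) |
| 1 | 7 / 14 / 28 (inside) | 8 / 15 / 29 (miss) | 9 / 16 / 30 (miss) |
| 2 | 6 / 13 / 27 (inside) | 7 / 14 / 28 (inside) | 8 / 15 / 29 (miss) |

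With d = 0 the +1 alone causes the miss. With d = 1 a one-day result lag is needed as well.

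**Effect on the landmarks.** The Day 7 rates of 25% (placebo) and 50% (active) are the plan's assumptions in SAP 4.1.2. The cumulative first-negative rates at T14 and T28 are assumed here. No censoring before Day 28 is assumed, so Kaplan-Meier equals the cumulative proportion.

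| Assumed clearance at T7 / T14 / T28 | Kaplan-Meier at Day 7 / 14 / 28 when on-time swabs miss |
|---|---|
| Placebo 25 / 55 / 85% | 0 / 25 / 55% |
| Active 50 / 75 / 95% | 0 / 50 / 75% |
| Placebo 25 / 60 / 90% | 0 / 25 / 60% |
| Active 50 / 80 / 95% | 0 / 50 / 80% |

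The Day 7 difference is 0 instead of 50 − 25 = 25 points, whichever later rates are assumed.

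**Visits not exactly on schedule.** No window is given for the swab visits. Suppose actual days fall −1, 0, +1 or +2 from nominal with equal probability, with d = 0 and L = 0. Only swabs one day early (1 in 4) then count at their own landmark. For placebo at 25 / 55 / 85%:

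- Day 7: 25 × 1/4 = 6.25%
- Day 14: 25 + (55 − 25) × 1/4 = 32.5%
- Day 28: 55 + (85 − 55) × 1/4 = 62.5%

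This is a blend of visits rather than a clean displacement by one.

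**Is dropping the +1 enough?** Take swab date minus randomisation date without +1, and the same spread. Swabs on time or one day early (2 in 4) now count. Placebo reads 25 × 1/2 = 12.5%, 25 + 30 × 1/2 = 40% and 55 + 30 × 1/2 = 70%, against 25 / 55 / 85% at the visits. Late swabs still miss.

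**NEWS/oxygen endpoint.** This assessment has no laboratory turnaround, so L = 0 is the natural reading. On-time assessments then miss only if d = 0.

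**The case against.** **First dose may not be on T0.** Protocol 5.1.3 has the treatment box brought to the home after randomisation, and the first treatment day needs both a morning and an evening dose. SAP 13.1 expects 4 capsules on the first day and 26 after it, which at two a day is 13 further days. With d = 1 the last dosing day is then day 14, the visit labelled end of treatment; with d = 0 it is day 13. On the other side, the protocol's schedule dispenses drug at T0, and SAP 3.1.1 describes day 7 as following 7 days of therapy. The documents do not settle it. This stands as a limit: the miss is conditional.

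**The result-date wording is ambiguous.** The confirmation wording also appears for the NEWS endpoint, where no laboratory is involved, and the PCR formula itself names the date of undetectable virus. It may mean the date of the assessment. If so, L = 0 and the miss requires d = 0. This too stands, and is a reason to name the date.

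**The inference is hardly touched.** A uniform shift keeps the order of events, so log-rank and Cox comparisons do not change. The primary analyses in SAP 14.1.1 do not use this derivation, and the correct visit proportions appear elsewhere in the report. This stands.

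**Counting from first dose as Day 1 is a legitimate convention.** So it is. The fault lies in reading that scale at day numbers from another one.

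**Conclusion.** The point holds in conditional form. If the first dose is on T0, on-time swabs are timed at 8, 15 and 29 or later and are not counted at Day 7, 14 and 28. More generally they miss when the result lag is at least the first-dose delay. Whether a swab counts at its own landmark thus depends on drug delivery and laboratory turnaround, for which the documents give no figures.

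Where on-time swabs miss, Day 7 reads about 0% in every arm and hides the assumed 25-point difference. Day 14 shows T7 clearance, and Day 28 shows cumulative clearance through T14. Figures beyond Day 7 rest on assumed rates, and visit spread would give a blend.

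Three stronger readings might be inferred and are not supported:

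- That every swab falls late. With d = 1 and a same-day result, the times are exactly 7, 14 and 28.
- That every landmark shows the preceding visit. No post-baseline swab precedes T7, so Day 7 shows no events rather than an earlier result.
- That the treatment comparisons are wrong. The primary day-7 and day-14 logistic analyses are untouched, and a uniform shift leaves log-rank and Cox unchanged while moving the reported quartiles by the same number of days. A result lag that varies between patients could alter the order of events, but nothing in the documents allows that to be sized.

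This is a defect in a reported secondary estimate, worth correcting because the correction costs so little.

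**What to change.** In SAP 14.1.3 and 4.4:

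1. Define the event date as the swab collection date, not the date of the PCR result.
2. State one time origin, consistent with endpoints counted from randomisation.
3. For the Kaplan-Meier landmarks, assign T7, T14 and T28 assessments the nominal times 7, 14 and 28, or define visit windows that do the same. Removing the +1 without this step is not enough, because late visits would still miss.
4. Apply the same rules to the NEWS/oxygen time endpoint, using the assessment date.

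A discrete-time or interval-censored analysis by visit is an optional alternative. It would also acknowledge that clearance is observed only at three swabs.

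The cost is SAP wording and derivation code. Section 6 of the protocol already has the sampling date entered in the eCRF, so no new data are needed. The change should be made before unblinding.
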